Study Protocol

Official Title: Visceral Manipulation in Patients With Chronic Low Back Pain

NCT03101020

Document Date: November, 18th 2016

Study Protocol

[figure not shown]
All participants received equal treatment during the assessments and conventional therapy. They were treated one time per week for five weeks. Each session took 50 minutes, starting with 40 minutes of conventional physiotherapy and finishing with 10 minutes of active or placebo visceral manipulation, depending on the participant's group allocation.

Conventional physiotherapy

[figure not shown]
We created a protocol of exercises for individuals with low back pain based on the clinical practice guidelines by Delitto *et al.* (2012). The protocol consisted of general exercises to mobilize, strength, and stabilize the spinal column, pelvis and hip, as it is described at Figure 1. All participants were oriented to keep an active lifestyle focusing on the activities they could perform (Koes *et al.* 2010; Panagopoulos *et al.* 2014).

At the end of the first session, the participants received a list with the description and photos of the exercises they performed during that session and that they would need to do every other day at home; however, there was no control if the participants performed the exercises at home. The criteria to progress the exercises were no pain, no fatigue, and no fear on performing it.

[figure not shown]
A

B

[figure not shown]
C

[figure not shown]
D

E (1)

E (2)

F (1)

[figure not shown]

F (2)

[figure not shown]

F (3)

[figure not shown]
G (1)

G (2)

[figure not shown]
G (3)

H (1)

H (2)

[figure not shown]
I (1)

I (2)

[figure not shown]
J (1)

J (2)

[figure not shown]
J (3)

K (1)

K (2)

L (1)

L (2)

Figure 2. Exercise protocol. **A** Erector spinae stretching, in dorsal decubitus pull the knee towards the abdomen – 2 sets of 30 seconds. **B** Knee rolls, roll the knees to one side and the other maintaining both shoulders on the floor – 2 sets of 10 seconds per side. **C** Piriformis stretch, in dorsal decubitus cross one ankle over the opposite knee and pull this leg towards the abdomen – 2 sets of 30 seconds per side. **D** Pelvic tilts, perform pelvic anteversion and retroversion – 10 to 15 repetitions. **E(1)** Back extensions, in ventral decubitus, extend the back supporting the upper body on flexed

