During all sessions, the participants had to remain in a hook-lying position and the head over a pillow to decrease the tension on the abdominal wall. A well-trained physiotherapist performed the visceral manipulation over eight spots on the abdomen. Each spot has a specific technique name, which are described in Figure 2, and each technique took 1 minute, except for the last two techniques that were performed 10 times each. For the experimental group (direct visceral manipulation), the therapist performed a deep pressure with the lower palm over those spots. The placebo visceral manipulation involved a light touch over the same spots, without intending to treat the patient, with the same amount of time and repetitions as the experimental group (McSweeney et al. 2012). At the end of the last session, the participants were asked to identify if the technique they received was the experimental or the placebo one.

[figure not shown]

Figure 3. Visceral manipulation protocol. Orientation of the pictures, cranial to the left and caudal to the right. **A** Cardia manipulation – 1 minute. **B** Pylorus manipulation – 1 minute. **C** Oddi sphincter manipulation – 1 minute. **D** Duodeno-jejunal valve manipulation – 1 minute. **E** Ileocecal valve manipulation - 1 minute. **F** Sigmoid colon manipulation – 1 minute. **G** Liver global manipulation – 10 repetitions. **H** Global hemodynamic manipulation – 10 repetitions with pressure during expiration and another 10 for inspiration.

Outcomes

All participants were assessed three times, pre-treatment, post-treatment and follow-up. Pre-treatment assessment was one week before the first session of treatment, post-treatment was right after the last session of treatment and the follow-up was one week after the last session of treatment. A team member, which was not involved with the interventions, was responsible for collecting all the baseline measures and outcomes.

Primary outcome

Pain intensity was evaluated through a Visual Analog Pain Scale of 11 points, where the participant choose a number from 0 to 10, 0 equals to “no pain at all” and 10 to “unbearable pain” (Childs *et al.*, 2005).

Secondary outcomes

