Statistical Plan

Official Title: Visceral Manipulation in Patients With Chronic Low Back Pain

NCT03101020

Document Date: November, 18th 2016

Statistical Analysis Plan

Intention to treat analysis was employed when necessary, with the data from the previous evaluation repeated to substitute missing data. The Kolmogorov-Sirmonov test demonstrated normal data distribution. Thus, parametric tests were performed and the data were expressed as mean and standard deviation. Two-way analysis of variance (ANOVA) was used to compare the effects of stimulation during motor training on the main outcome variables and the Bonferroni correction for multiple comparisons was employed as the post hoc test. The dependent variables were pain intensity, lumbar mobility, general functionality and specific functionality. The independent fixed variables were treatment (baseline, posttreatment and follow-up), group (experimental group and control group) and group-treatment interaction. The Pearson correlation test verified the correlation between the outcomes of the variables. A p-value <0.05 indicated a statistically significant result. The data were organized and tabulated using the Statistical Package for Social Sciences (v.19.0).

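### Baseline pain enters the ANOVA only as a level of time; using it as a covariate would sharpen the between-group estimate at no data cost

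*SAP*

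**What the plan says.** The protocol's Primary outcome section names pain: "Pain intensity was evaluated through a Visual Analog Pain Scale of 11 points". Its Outcomes section sets the visits: "All participants were assessed three times, pre-treatment, post-treatment and follow-up". It places the two later ones close together: "post-treatment was right after the last session of treatment and the follow-up was one week after the last session of treatment". Neither is called primary. The groups differ in the last part of each session: "10 minutes of active or placebo visceral manipulation, depending on the participant's group allocation".

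The SAP is a single paragraph covering four dependent variables, with pain not singled out. The method is given as "Two-way analysis of variance (ANOVA) was used to compare the effects of stimulation during motor training on the main outcome variables", with these terms: "The independent fixed variables were treatment (baseline, posttreatment and follow-up), group (experimental group and control group) and group-treatment interaction". The factor called treatment is time. For follow-up tests, "the Bonferroni correction for multiple comparisons was employed as the post hoc test"; the pairs are not listed. Missing values are filled "with the data from the previous evaluation repeated to substitute missing data". The 0.05 threshold is attached to no particular term or visit. The SAP does not say that the ANOVA is a repeated-measures one, and neither document names a covariate.

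**The concern.** The trial asks whether active manipulation lowers pain more than placebo. A reader will want a between-group difference with a confidence interval, and the plan as written does not produce one. The interaction tests whether the groups' profiles over three visits differ in any way. It does not say at which visit or by how much.

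Baseline pain is measured on everyone, but the ANOVA uses it only as another outcome level. Any contrast from the interaction then takes account of baseline by subtraction, which is less efficient than regressing on it. A plain comparison at one visit takes no account of it. The group main effect, if anyone relied on it, would average in a visit at which no treatment effect can exist. What is at stake is the precision and readability of the primary result.

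**Working it through.** **Inputs.** The documents give no sample size, SD, expected effect or correlation, so there is no planned figure to reproduce. Assumptions for illustration: 30 per arm, unit SD, effect 0.6 SD, two-sided 0.05, and correlation ρ between baseline and a later score of 0.3, 0.5, 0.7 or 0.8.

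**One visit, 1 df.** Relative variance of the group difference:
- unadjusted: 1
- change from baseline (the interaction contrast for that visit): 2(1−ρ)
- ANCOVA on baseline: 1−ρ²

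The ratio of ANCOVA to change is (1−ρ²)/[2(1−ρ)] = (1+ρ)/2. The ratio of ANCOVA to unadjusted is 1−ρ².

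| ρ | ANCOVA variance below change | ANCOVA variance below unadjusted | Power: unadjusted / change / ANCOVA | 95% CI half-width (SD): unadjusted / change / ANCOVA |
|---|---|---|---|---|
| 0.3 | 35% | 9% | 63 / 49 / 67% | 0.52 / 0.61 / 0.49 |
| 0.5 | 25% | 25% | 63 / 63 / 75% | 0.52 / 0.52 / 0.45 |
| 0.7 | 15% | 49% | 63 / 84 / 89% | 0.52 / 0.40 / 0.37 |
| 0.8 | 10% | 64% | 63 / 95 / 97% | 0.52 / 0.33 / 0.31 |

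The powers are before any Bonferroni correction. The loss against the change score shrinks as ρ rises; the loss of the unadjusted comparison grows.

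**Group main effect.** With a true difference of 0 at baseline and d at both later visits, it estimates (0+d+d)/3 = 2d/3, with relative variance (1+2ρ)/3 under equal correlations. At d = 0.6 its power is 55/46/40/37%.

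**Both visits, 2 df, equal correlations.** Take group differences m = (0, e₁, e₂) at the three visits.
- Repeated-measures interaction: noncentrality n·Σ(m−m̄)²/[2(1−ρ)].
- Joint test of group at both later visits, adjusted for baseline: noncentrality (n/2)·e′S⁻¹e, where S is the covariance of the later scores given baseline.

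Example at ρ = 0.5, e = (0.6, 0.6). Interaction: m̄ = 0.4, Σ = 0.16+0.04+0.04 = 0.24, so 30×0.24/1 = 7.2. Joint: S has 0.75 on the diagonal and 0.25 off it, so e′S⁻¹e = 0.36×2/(0.75+0.25) = 0.72, and 15×0.72 = 10.8.

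| Effects at the two visits (SD) | Interaction, ρ = 0.3/0.5/0.7/0.8 | Adjusted joint test |
|---|---|---|
| 0.6 and 0.6 | 51/66/87/97% | 78/82/93/98% |
| 0.3 and 0.6, either order | 39/53/76/91% | 59/66/82/93% |
| 0.6 at one visit only | 51/66/87/97% | 58/70/88/97% |

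**Both visits, unequal correlations.** The later visits are one week apart. Baseline is taken a week before a course of five weekly sessions, so the two later scores may well correlate more with each other than with baseline. The joint test is again by formula, with off-diagonal of S equal to the between-visit correlation minus ρ². The interaction is from 4,000 simulated trials.

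| Correlation with baseline / between later visits | Effects (SD) | Interaction | Adjusted joint test |
|---|---|---|---|
| 0.5 / 0.8 | 0.6 and 0.6 | 70% | 71% |
| 0.7 / 0.9 | 0.6 and 0.6 | 89% | 86% |
| 0.5 / 0.8 | 0.3 and 0.6 | 59% | 70% |

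For the first row, e′S⁻¹e = 0.36×2/(0.75+0.55) = 0.554, and 15×0.554 = 8.3, against 10.8 under equal correlations. In these settings the uncorrected interaction F test also rejects about 6% of the time when there is no effect, so its power is slightly flattered.

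**The case against.** The strongest reply is that the plan already has a serviceable test. The interaction is listed by name, Bonferroni comparisons follow it, and testing the interaction first is how most statisticians would read the paragraph. Fitted as repeated measures, it is valid and uses baseline. Choosing a covariate instead is a matter of efficiency, and the efficiency gain is small if ρ is high. All of that stands. So does the point about correlations: the equal-effects advantage of the joint test is not general.

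The reply does not remove two facts. The interaction yields no single group difference, and at a given visit ANCOVA is more precise than the change score for any ρ below 1.

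Four stronger readings are tempting, and the documents do not support them.
- A reader might infer that the analysis is invalid or biased. It is neither, provided allocation was random and the repeated structure was fitted. The SAP is silent on the second of these. The supplied text says only that groups were allocated, so randomness is a condition here and not something the text disproves.
- A reader might infer an inflated false-positive rate because no term is designated. If either the main effect or the interaction could count, the chance of p<0.05 with no effect is about 9.5 to 10%. If uncorrected comparisons at both visits also counted, it is about 13 to 14%. But the SAP does not say that any of several results would be accepted, and the Bonferroni step would lower the second figure.
- A reader might infer that the diluted main effect decides the trial. The SAP lists that term but does not say so.
- A reader might infer that baseline adjustment always raises power over the planned test. The 0.7/0.9 case shows otherwise.

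**Conclusion.** The point holds as an improvement the sponsor should make, not as an error that undermines the result. Baseline is used only as a time level, no covariate is named, and the natural deciding term does not give a between-group estimate.

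The firm part of the size is at one visit: variance 10 to 35% lower than the change score and 9 to 64% lower than an unadjusted comparison, for ρ from 0.3 to 0.8. These ratios need equal variances over time and random allocation, but no sample size or effect size.

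The two-visit powers are conditional. They rest on an assumed 30 per arm and 0.6 SD. With equal effects, the advantage of the joint test depends on the later visits being no more correlated with each other than with baseline. In the unequal-correlation case worked with different effects, the joint test stays ahead.

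**What to change.** For each outcome, model the post-treatment and follow-up scores on group, visit, group-by-visit, baseline and baseline-by-visit, with participant as the repeated unit. Use observed post-baseline scores: a missing post-treatment value filled from the previous assessment would equal its own covariate.

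For pain, report the baseline-adjusted group difference at each visit with a 95% CI, and make the 2-df joint test of group the primary test. The joint test should lead because a single visit can be the wrong one. With 0.3 SD post-treatment and 0.6 SD at follow-up (equal correlations), ANCOVA at post-treatment alone has 22/26/36/48% power, against 39/53/76/91% for the planned interaction. Name one primary visit only if the choice is made without sight of outcome data. The SAP reports the result of a normality test in the past tense, which suggests that the data had been examined.

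No new data are needed, since baseline is already collected. If the analysis has not been run, the cost is a change of SAP text and model code. If it has, this is a re-analysis and must be labelled as one.

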Lumbar spine mobility was assessed through the original Schober Test. Roland-Morris Disability Questionnaire was used for General functionality and Patient Specific Functional Scale was used for Specific functionality (Tousignant *et al.* 2005; Nusbaum *et al.* 2001; Kowalchuk-Horn *et al.*, 2011; Oliveira *et al.*, 2008; Stratford *et al.*, 1995).

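### Pain is the only primary outcome, but the SAP names no decisive ANOVA term or contrast for it and does not say that the model is repeated-measures

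*SAP*

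**What the plan says.** **Protocol.** One measure stands under Primary outcome: "Pain intensity was evaluated through a Visual Analog Pain Scale of 11 points". Mobility ("Lumbar spine mobility was assessed through the original Schober Test") and the two function scales stand under Secondary outcomes. On timing, the Outcomes section says "All participants were assessed three times, pre-treatment, post-treatment and follow-up", and that "post-treatment was right after the last session of treatment and the follow-up was one week after the last session of treatment". Neither later visit is called primary.

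**SAP.** The comparison is introduced as "Two-way analysis of variance (ANOVA) was used to compare the effects of stimulation during motor training on the main outcome variables". The outcomes are listed without rank: "The dependent variables were pain intensity, lumbar mobility, general functionality and specific functionality". The model is then set out: "The independent fixed variables were treatment (baseline, posttreatment and follow-up), group (experimental group and control group) and group-treatment interaction". The factor called treatment is therefore time, and baseline is one of its three levels. On multiplicity the SAP says that "the Bonferroni correction for multiple comparisons was employed as the post hoc test", without saying which comparisons form the family. Significance is a p-value below 0.05, tied to no particular term.

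**The concern.** The protocol settles which outcome matters most. What remains open is which test on that outcome gives the trial's answer. The model has two terms that involve the arms, group and group-by-time, and they ask different questions. One can be significant when the other is not, so two analysts following the SAP could report different conclusions on pain from the same data.

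The SAP also does not say that the three scores per participant are handled as repeated measures, and this determines the error rate of both terms. The one sentence that could have named the comparison refers to stimulation and motor training, whereas this trial compares active with placebo visceral manipulation.

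At stake are the false-positive rate behind the main conclusion and whether the trial yields one interpretable estimate of the pain difference.

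**Working it through.** **Inputs from the documents.** Two groups; three visits including baseline; one primary outcome; threshold 0.05. There is no sample size, SD, target effect or power statement, so the plan has no figure to reproduce.

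**Assumptions.** Random allocation, equal SD at each visit and, unless stated otherwise, the same correlation r between any two visits, with r = 0.3, 0.5 or 0.7. Simulations use 30 per arm.

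**1. What the group term estimates.** With a true difference d at both later visits and none at baseline, it estimates (0 + d + d)/3 = 0.67d. With no treatment effect but a 1-point chance difference at baseline, its expected value is (1 + r + r)/3 = 0.53, 0.67 or 0.80 points. Over all possible allocations this averages to zero. With correct error terms the test keeps its 5% (simulated 4.9%), so the cost is precision, not bias.

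**2. What the interaction tests.** Two groups by three visits gives (2−1)(3−1) = 2 degrees of freedom. It is one joint test of two contrasts and does not give a single between-group difference.

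**3. If either term may count.** In a balanced repeated-measures ANOVA under the assumed correlation pattern, the two tests are independent under the null: 1 − 0.95² = 0.0975. Simulation with 40,000 trials per setting gives 9.5 to 9.7%. With one named term the rate is 5%.

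**4. If visits were treated as independent.** The variance of a participant's three-visit mean is σ²(1 + 2r)/3, but an ordinary two-way ANOVA uses σ²/3. The group term's large-sample false-positive rate is P(|Z| > 1.96/√(1 + 2r)):
- r = 0.3: 1.96/√1.6 = 1.55, giving 12.1%
- r = 0.5: 1.96/√2.0 = 1.39, giving 16.6%
- r = 0.7: 1.96/√2.4 = 1.27, giving 20.6%

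Simulation gives 11.8, 16.5 and 20.3%. The interaction becomes conservative: 1.4, 0.3 and 0.01%.

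**5. How often the verdicts differ (illustrative).** Share of trials in which exactly one of the two terms is significant, repeated-measures ANOVA, effect equal at both later visits:

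| True difference (SD) | r = 0.3 | r = 0.5 | r = 0.7 |
|---|---|---|---|
| 0 | 9–10% | 9–10% | 9–10% |
| 0.708 / 0.643 / 0.530* | 44% | 50% | 60% |
| 0.8 | 34% | 34% | 38% |
| 1.0 | 13% | 14% | 19% |
| 1.2 | 3% | 4% | 7% |

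*Chosen so that a baseline-adjusted test at one visit has 80% power. At that effect, power is 69/51/32% for group, 65/72/78% for the interaction, and 95/93/91% for the baseline-adjusted mean of the two later visits.

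**6. How far averaging helps.** Let s be the correlation between the two later visits. Patients needed relative to a one-visit baseline-adjusted test are [(1 + s)/2 − r²]/(1 − r²). With r = s = 0.5 this is (0.75 − 0.25)/0.75 = 0.67. With r = 0.5 and s = 0.8 it is (0.90 − 0.25)/0.75 = 0.87, and with s = 0.9 it is 0.93. The later visits are only a week apart, so the smaller saving is plausible. Under that pattern an uncorrected interaction test has about 6 to 7% false positives.

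**7. When averaging hurts.** If the effect exists at one later visit only, the averaged test has 43/40/38% power where a test at that visit has 80%.

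**The case against.** **The usual reading.** Many readers would take the interaction as the efficacy test and a two-way ANOVA over visits as repeated-measures. The term fixed variables is compatible with a model that also has a random subject effect. The SAP nowhere says that the group term counts as efficacy, or that visits were independent. This stands: the 10% and the 12 to 20% are conditional, and a reader who takes either as this trial's actual error rate goes beyond the text. It does not close the gap, because the SAP does not state the usual reading either.

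**Ranking of outcomes.** A reader might infer that a win on any of the four outcomes could count. The protocol names one primary outcome and the SAP does not contradict it, so no four-outcome error rate is claimed.

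**Bias.** A reader might infer that including baseline biases the group comparison. With random allocation and correct error terms it does not. The 1-point illustration is also not a typical event: at 30 per arm, a chance baseline difference of at least 1 point has probability about 1, 5, 12 or 20% for an assumed SD of 1.5, 2, 2.5 or 3.

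**Disagreement.** The highest figures belong to one chosen effect size and fall to single digits for large effects. Verdicts that differ means one term significant and the other not, not effects in opposite directions.

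**Bonferroni.** It applies to post hoc comparisons only. It does not choose between the group term and the interaction.

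**Conclusion.** The point holds as a gap in the decision rule for the primary outcome, and it should be fixed. Three parts need no assumed sample size: no decisive term or contrast is named for pain; the group term shows two thirds of an effect that is equal at both later visits; and the interaction gives no single estimate. The false-positive rate is about 10% if either term may count, and about 12 to 20% for the group term alone if visits were treated as independent (r from 0.3 to 0.7, assumed). The documents establish neither condition.

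For effects equal at both later visits, the two terms differ in roughly 3 to 60% of trials at an assumed 30 per arm, depending on effect size and correlation. That range and the power and sample-size figures illustrate the problem; they are not estimates for this trial.

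The SAP is written in the past tense and already reports a normality result. A reader might infer that the analysis was chosen after the data were seen. The documents do not establish that, but it affects how any choice made now must be labelled.

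**What to change.** Name one decisive test for pain: the baseline-adjusted experimental-minus-placebo difference, averaged over the two post-baseline visits, from a repeated-measures model that accounts for within-patient correlation, two-sided at 0.05 with its 95% confidence interval. This avoids choosing a visit and gives one estimate in points on the pain scale.

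Report the group main effect including baseline, the time effect and the interaction as supportive only. Treat the two single-visit between-group differences as secondary, with Bonferroni over those two (0.05/2 = 0.025 each). Replace the reference to stimulation and motor training with this trial's own comparison.

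**Cost.** SAP wording and one re-analysis of pain scores already collected; no new data. The averaged test loses power if the benefit exists at one visit only (about 38 to 43% against 80%, on the assumptions above). If data had been seen when the test was chosen, it must be labelled post hoc, and naming it cannot then restore a clean 5%.

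### The SAP calls the visit factor treatment, describes an intervention this trial does not have, and does not say which term tests visceral manipulation

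*SAP*

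**What the plan says.** The Statistical Analysis Plan gives the purpose of the analysis as follows: "Two-way analysis of variance (ANOVA) was used to compare the effects of stimulation during motor training on the main outcome variables". It then lists the model terms: "The independent fixed variables were treatment (baseline, posttreatment and follow-up), group (experimental group and control group) and group-treatment interaction". Bonferroni is named as the post hoc correction, without saying which comparisons it covers. One threshold, p below 0.05, is given and tied to no particular term.

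The Protocol describes a different comparison. Its opening paragraph says "All participants received equal treatment during the assessments and conventional therapy", with each session "starting with 40 minutes of conventional physiotherapy and finishing with 10 minutes of active or placebo visceral manipulation". Under Visceral manipulation it defines the two arms. In one, "For the experimental group (direct visceral manipulation), the therapist performed a deep pressure with the lower palm over those spots". In the other, "The placebo visceral manipulation involved a light touch over the same spots, without intending to treat the patient". Under Outcomes it gives the measurement schedule: "All participants were assessed three times, pre-treatment, post-treatment and follow-up". These three assessments are the levels of the factor that the SAP calls treatment.

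**The concern.** Two labels in the SAP point away from the trial's question. The purpose sentence names stimulation and motor training, and neither appears in the Protocol. The word treatment is attached to time, while the factor that separates deep pressure from light touch is called group.

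Someone looking for the treatment effect in the ANOVA table is led by name to the visit row. That row pools both arms. It contains everything that moves pain over the study in all participants: natural course, regression to the mean after entry, five physiotherapy sessions, home exercise and placebo response. It also contains part of any real effect of manipulation, mixed in with the rest.

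The post hoc step adds to the risk. Visit is the only main-effect factor with more than two levels, so an unspecified Bonferroni procedure most naturally falls on comparisons between visits. At stake is a report that credits manipulation with an improvement both arms had.

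**Working it through.** The documents give no sample size, SD, effect size or allocation ratio, so there is no planned figure to reproduce. The check has two parts: what each term estimates, and how often it is significant under assumed inputs.

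**What each term estimates.** Let pain improve from baseline by C points in the placebo arm and by C + D in the experimental arm, at both later visits, with equal arms and the same baseline mean. D is the effect of manipulation.

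- Visit main effect (called treatment in the SAP), post-treatment against baseline: [C + (C + D)]/2 = C + D/2.
- Group-by-visit interaction, difference between arms in that change: (C + D) − C = D.
- Group main effect, averaged over three visits: (0 + D + D)/3 = 2D/3, because the baseline visit is included.

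| C | D | Visit effect, C + D/2 | Interaction, D |
|---|---|---|---|
| 2 | 0 | 2 | 0 |
| 0 | 2 | 1 | 2 |
| 2 | 2 | 3 | 2 |

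**How often each is significant.** Inputs from the documents: two arms, three visits, threshold 0.05 (SAP; Protocol, Outcomes). Assumptions: n = 10, 20 or 30 per arm, SD σ = 2 points, correlation ρ = 0.5 between visits, C = 1 or 2 points, and participants as the error stratum (a repeated-measures F test).

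With D = 0, the visit pattern (0, −C, −C) has squared deviations from its mean summing to (4/9 + 1/9 + 1/9)C² = (2/3)C². The noncentrality is λ = 2n × (2/3)C² / [σ²(1 − ρ)], on 2 and 2(2n − 2) degrees of freedom.

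- n = 20, C = 1: λ = 40 × 0.667 / 2 = 13.33 on 2 and 76 df, critical F 3.12, significant in 90% of trials.
- n = 20, C = 2: λ = 53.33, significant in essentially 100%.

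Simulation with 20,000 trials per setting agrees with these figures and gives the interaction rates:

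| n per arm | Visit term, C = 1, D = 0 | Visit term, C = 2, D = 0 | Interaction, D = 0 |
|---|---|---|---|
| 10 | 59% | 99.6% | about 5% |
| 20 | 90% | 100% | about 5% |
| 30 | 98% | 100% | about 5% |

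The result depends on ρ. For n = 20 and C = 1, ρ = 0.3 gives λ = 9.52 and 78%; ρ = 0.7 gives λ = 22.22 and 99%.

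**The reverse case.** With C = 0 and D = 2, only manipulation works. The visit effect is then D/2 = 1 point, and the visit term is significant in 59%, 90% and 98% of trials (n = 10, 20, 30), the same as with C = 1 and D = 0. The visit row cannot tell these two situations apart. The interaction can: about 5% when D = 0, against 59%, 90% and 98% when D = 2.

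**The case against.** The strongest reply is that the sentence naming the factors also lists group and the group-by-treatment interaction. That interaction is the between-arm test of change, so the planned model does contain a valid test of manipulation. The SAP also prints the levels of its treatment factor in brackets, so a careful reader can see that it means visit. All of this stands, and it rules out several stronger readings.

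- A reader might infer that the SAP never tests manipulation. It does, through the interaction.
- A reader might infer that the term called treatment says nothing about manipulation. With equal arms it contains D/2; the trouble is that this cannot be separated from C.
- A reader might infer that the SAP makes this main effect the test of efficacy. It does not; it gives no term that role.
- A reader might infer that the post hoc tests are baseline-to-post comparisons inside each arm. The SAP does not say whether they are within or between arms, so any rate for one arm reaching significance while the other does not would rest on a procedure the documents do not describe.
- A reader might take the 90% to 100% as a false-positive rate. It is not: when everyone improves, a significant change over time is a correct finding about time. It becomes an error only if credited to manipulation.

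What the reply does not remove is the gap itself. Nothing in the SAP directs the reader to the interaction, the stated purpose belongs to some other comparison, and the name treatment sits on the wrong row.

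**Conclusion.** The concern holds as a defect of specification and labelling, with a real consequence for interpretation. The SAP misnames the visit factor, states a comparison that is not this trial's, and leaves open which term and which post hoc contrasts bear on visceral manipulation. A significant result for the term called treatment is no evidence for manipulation.

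The algebra (C + D/2 against D) needs only equal arms and equal baseline means. The percentages rest on assumed inputs: with no manipulation effect, 20 per arm, SD 2, correlation 0.5 and a shared improvement of 1 to 2 points, the visit term is significant in about 90% to 100% of trials and the interaction in about 5%. The lower end falls to 59% with 10 per arm and to 78% with correlation 0.3.

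The 5% also assumes that the analysis treats visits as repeated measures on the same participant. The SAP mentions only fixed factors. If the visits were analysed as independent observations, the interaction would reject in only about 0.2% to 0.4% of trials under the same assumptions with D = 0.

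**What to change.** Amend the Statistical Analysis Plan, and carry the same labels into the results tables:

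1. Rename the factor *visit*.
2. Replace the purpose sentence with the actual comparison: visceral manipulation plus conventional physiotherapy versus placebo manipulation plus conventional physiotherapy.
3. State that the conclusion about manipulation rests on the group-by-visit interaction for pain intensity, the Protocol's primary outcome, and that visits are repeated measures within participant.
4. Apply the Bonferroni comparisons to between-arm differences in change from baseline.
5. State that the visit main effect and any within-arm changes are descriptive and support no conclusion about manipulation.

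This changes SAP wording only and needs no new data. The cost is fewer significant results to report, since change over time would no longer count as a treatment finding.
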